After surgery objective assessments will be documented including postoperative complications, blood loss, fetal outcome. The surgeon will fill out a survey investigating the surgeons' impression. Directly after child delivery patients will be first asked about the pain sensation during the delivery according to a VAS scale. Postoperatively at 4-6 hours after the surgery, patients will fill out the first survey. At day 1 and day 2 postoperatively, patients will fill out the following surveys. Data, which is collected from the surveys, will be encoded pseudo-anonymous. Recording of the complications will be performed in the first 3 days after delivery, as the usual hospital stay ranges between 3-5 days. This period covers all usual postoperative complications. Recording postpartum pain medications is essential as we cannot predict who will require which level of pain relievers (mild analgesics without opioids, weak opioids and strong opioids).

The aim of this study is to evaluate if the mother's active pushing during the C-section reduces pain during child delivery

Primary endpoints

- The severity of the intraoperative pain

Secondary endpoints:

- The severity of the postoperative pain
- Patient's satisfaction with the operation and her participation
- Patient's psychological status postoperatively
- Breastfeeding after early Skin to Skin contact (SSC)
- Neonatal Outcome
- Duration of the hospital stay, duration of the surgery and its complications (intraoperative Haemorrhage, wound complication, PPH and surgical injury)
- Surgeon's satisfaction with the procedure

The data collection and documentation

Data will be collected after taking the patient's written informed consent. Patients will be given pseudonyms. Only the study leader will have access to the files.

Data privacy:

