Before a patient is enrolled in the study, written informed consent will be collected with the patient's verbal acceptance and signature to join the study. No personal or identifiable data will be published or passed on to third parties. The approval of the participants can be cancelled at any time. This cancellation will not influence further medical care. In the event of a dropout, the patient's data will be deleted and will not be included in the analysis. The data will only be used for scientific purposes. The results will be published in research reports, posters and scientific publications in accordance with the Data protection and privacy policy. The collected data will be archived for 10 years.

Unwanted events

There are no expected specific complications regarding this technique since both techniques are routinely used. However, potential surgical complications associated with cesarean section are:

- Maternal complication (Endometritis, wound complication, haemorrhage, infection, surgical injury of the urinary bladder, the small intestine and rarely the ureter), thromboembolism, ileus, septic pelvic thrombophlebitis and rarely hysterectomy
- Fetal and neonatal risks (iatrogenic prematurity, iatrogenic birth trauma, transient tachypnoea of the newborn and neonatal adaption syndrome)
- Anaesthetic complications.
- Complications regarding the Valsalva manoeuvre are only described for prolonged pushing during vaginal delivery. These complications are very unlikely during C-section. (11)

Only patients with indicated C-section will be included. Thereby, patients will not be exposed to additional risk as described above compared to vaginal delivery.

Evaluation /Biometrics

Descriptive statistics will be used to assess patients characteristics. Student T-test or Mann Whitney U test will be used to for continuous data to compare parametric or nonparametric data sets, respectively and the chi-square test will be applied for categorical data.

The primary evaluation should be based on the intention-to-treat population, i.e. all patients who were randomized will be included in the evaluation. With regard to the primary end point, a very timely recording will take place, so that only a negligible number of missing values can be assumed.

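### Complications are recorded only to day 3, the shortest usual stay, so later in-hospital events go uncounted in a secondary safety endpoint

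*Combined protocol and SAP*

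**What the plan says.** The Methods section of the combined protocol and SAP sets the recording period and its reason together: "Recording of the complications will be performed in the first 3 days after delivery, as the usual hospital stay ranges between 3-5 days". The next sentence adds: "This period covers all usual postoperative complications". No figure or source is given for that.

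The secondary endpoints put length of stay and complications on one line: "Duration of the hospital stay, duration of the surgery and its complications (intraoperative Haemorrhage, wound complication, PPH and surgical injury". The same four complications appear as item 5 of the list under Measurements, findings and observations.

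The Unwanted events section gives a longer list of possible caesarean complications. It opens "Maternal complication (Endometritis, wound complication, haemorrhage, infection, surgical injury of the urinary bladder" and goes on to thromboembolism, ileus and septic pelvic thrombophlebitis.

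The last patient survey is on day 2. Nothing in the document provides for recording complications after day 3, at discharge or after discharge.

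**The concern.** The reason offered does not lead to the window chosen. A usual stay of up to 5 days gives no ground for stopping at day 3 when some women are still in hospital. The length-of-stay endpoint already requires each woman's discharge date, so the two parts of one endpoint line are observed over different periods. A prolonged stay would be counted, while a day-4 or day-5 complication that caused it would not.

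What is at stake is the completeness of the maternal safety data. Both arms' complication rates would be understated by an unknown amount, and a real difference in later events would be harder to see.

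**Working it through.** **1. The plan's own figure.** The only calculated figure is the sample size for intraoperative pain: difference 0.8, SD 2, two-sided 0.05, 80% power (Power calculations). With n = 2(1.960 + 0.842)² × 2² / 0.8² = 98.1, rounded up, the normal approximation needs 99 per arm. The t-test gives 99.08, which rounds up to 100. The stated 100 per arm reproduces, and this point does not touch it.

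**2. The unobserved period.** The window ends on day 3 and the usual stay ends between day 3 and day 5. Unrecorded in-hospital time is therefore 3 − 3 = 0 days for the shortest usual stay and 5 − 3 = 2 days for the longest.

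**3. Which events are exposed.** Of the four named endpoint components:

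- Intraoperative haemorrhage and surgical injury arise at the operation and are not exposed.
- Wound complication is exposed.
- PPH is exposed only where it occurs late.

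Endometritis, infection, thromboembolism and similar events are in the Unwanted events list but are not named in the endpoint. They matter for a full safety account, less for the endpoint as defined.

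**4. What under-counting could cost.** The documents give neither complication rates nor their timing, so everything in this step is assumed. Let a fraction s of events fall after day 3 in both arms. Observed rates are then (1 − s) times the true rates. Power is that of the uncorrected chi-square test (the plan's test for categorical data) at two-sided 0.05 with 100 per arm. It is computed exactly as the sum, over all pairs (x, y), of Bin(x; 100, (1 − s)p₁) × Bin(y; 100, (1 − s)p₂) for which

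χ² = ((x − y)/100)² / (2p̄(1 − p̄)/100) > 3.84, with p̄ = (x + y)/200.

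| Assumed true rates | Expected events in 200 women | s = 0 | s = 20% | s = 40% | s = 50% |
|---|---|---|---|---|---|
| 5% v 15% | 20 | 68.3% | 57.2% | 42.9% | 35.0% |
| 10% v 20% | 30 | 51.8% | 42.1% | 32.4% | 27.0% |
| 5% v 10% | 15 | 27.0% | 21.1% | 15.4% | 13.2% |

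Expected events lost equal s times the total. At s = 20% and 50% that is 4 and 10 of 20, 6 and 15 of 30, and 3 and 7.5 of 15.

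Because s is applied to all events, while two of the four components cannot be late, s = 50% would need a large share of the total to be late wound complications or late PPH. The upper end of the range is therefore a severe case.

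**The case against.** The best defence is that day 3 was chosen because it is the last day on which nearly every usual-stay patient is still in hospital, so all women are observed for the same time. That stands. A common window is a sound basis for comparing arms, and the day-3 count should be kept for that reason.

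A reader might infer that the 5-day stay contradicts the statement that three days covers all usual complications. It does not. Length of stay says nothing about when complications arise, so both sentences could be true. The coverage statement is simply unsupported.

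A reader might also infer that the short window biases the comparison or hides harm in the pushing arm. The documents do not support that: the window is identical in both arms, and nothing in them suggests that late events would differ by arm. The Unwanted events section expects no complications specific to the technique.

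The power figures carry limited weight too. The trial was sized for pain only and claims no power for complications. At 5% v 10%, power is 27% even with complete capture, so at such rates the window is not the main limit on what the trial can show.

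Finally, recording to discharge makes observation time depend on length of stay, itself an endpoint, and adds nothing for women who leave on day 3. A common fixed window extending beyond the usual stay would be cleaner, but it would require contact after discharge. These points limit the concern without removing it: in-hospital events on days 4-5 still have no planned record.

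**Conclusion.** The point holds as a minor one. By its stated rule, the plan leaves up to two in-hospital days without a complication record, and its claim that nothing usual is missed has no figure or source. The consequence is under-counting and lost precision for wound complications, later PPH and the other later events listed under Unwanted events. That is part of one secondary safety endpoint. Bias between arms does not follow, and the primary endpoint and sample size are untouched.

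The size cannot be determined from the documents. Under the assumed rates and 20% to 50% loss, the fall in power runs from about 6 points (5% v 10%, 27.0% to 21.1%) to about 33 points (5% v 15%, 68.3% to 35.0%). The direction does not depend on those assumptions, since uncaptured events lower the count. That every woman is followed clinically to discharge, and that day 4-5 events would be in her chart, is inferred from the length-of-stay endpoint and is not stated.

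**What to change.** Make three changes to the text:

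- Abstract complications from the hospital chart to discharge for every woman, with the date of each event.
- Keep the day-3 count as the equal-window comparison between arms, and report the to-discharge count beside it, by arm, as descriptive safety data.
- Remove the statement that three days covers all usual complications, or limit it to what can be supported.

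The cost is a little more chart abstraction, up to two further days for a woman with a 5-day stay, with no extra visit or procedure. Follow-up in the to-discharge count will vary with length of stay, which is why it should remain descriptive. Events after discharge will still be missed, and the report should say so.

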1. Intraoperative and Postoperative pain at different time points (day 0,1,2 postoperatively) depending on validated numerical pain Scale (7).
2. Psychological status and the satisfaction of the patient postoperatively using the validated Edinburgh Postnatal Depression Scale (EPDS)(8).
3. Neonatal outcome according to APGAR score and pH Level from the umbilical cord.
4. the breastfeeding depending on Breastfeeding Self-Efficacy Scale, Short Form (BSES-SF) (9)(10).
5. The duration of the surgery and its complications (intraoperative haemorrhage, wound complication, postpartum haemorrhage (PPH) and surgical injury).
6. A surgeon questionnaire evaluating the actual performance of the procedure.

A detailed description of the course of study

Antenatally, pregnant women will be evaluated for their eligibility for this study. Patients planned for primary C-section will be informed on preoperative visits. (category 3&4 NICE guidelines). If so, written informed consent will be collected from the patients prior to their participation in this study. Patients will be informed about the postoperative assessment in order to evaluate the effects of C-section techniques. As described in the patient information, there will be general information about the procedure and that communication and maternal participation will be evaluated. An explanation of pushing or not-pushing, which both represent standard-techniques, will not be provided in

detail, to avoid expectation bias. Patients will be randomized by the study assistant using a 1:1 strategy. Patients will be assigned an identifier number upon their enrolment to the study. The allocation of participants, to either the control or the test group, will be randomly allocated using R software. This is to eliminate any human interference or bias in patients allocation.

All participating surgeons will attend specialized training during which the study principles and the variations in C-section technique will be explained. Directly before surgery, surgeons will be informed about the randomization results.

Control group: non-pushing

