In case of doubt or missing values, it will be replaced by the maximum observed VAS values in the study, which is a relatively simple elimination procedure and is easy to implement. As sensitivity analyses other imputation methods will be performed.

We will conduct ANCOVA analyses to see how postoperative pain medication influences the study outcome. The WHO pain medication scale will be used to group the patients.

Power calculations

Biometric Analysis was performed with the kind assistance of [name], Institut für Biometrie ,MHH. Please see the attached document.

There is a study from Berlin (6) on the subject, but this analysed a self-created composite variable on satisfaction and did not evaluate the sensation of pain separately. There are no known studies which assessed the intraoperative pain during child delivery. The best approximation remains the direct postoperative pain. An older study (12) was a randomized four-therapy-arm study (placebo, diclofenac, propacetamol or diclofenac and paracetamol directly after delivery) which assessed postoperative pain after caesarean section at several time points. This study reflects the routine pain medication used in our clinics and was therefore selected.

In the study analysing postoperative pain after caesarean section the mean VAS scores at 6 hours ranged between 3.4 and 3.9 with a standard deviation of 1.7-2.0. Since we want to evaluate intraoperative pain, we expect higher mean VAS scores between 6-7. We will calculate with a standard deviation of 2.0. Based on the findings of Armbrust et al and our clinical experience we expect a therapeutic effect of 15-20% which results in a mean VAS reduction of 0.8. Applying a two-sided T-Test for independent samples at a significance level of 0.05, a mean difference of 0.8 between the groups and a standard deviation of 2, we will need 100 patients per treatment arm to detect a difference between both treatment groups with a power of 80%.

There is currently no prognostic factor that is known in advance to influence outcome in a certain direction. Thus, stratification is not planned.

+

References:

1. Wacker J. Geburtshilfe. Kaiserschnitt vs. Natürliche Geburt. Geburtshilfe Frauenheilkd. 2010;70(10):840–3.
2. Beckmann M W, Bader W Bl. Finanzierung und finanzielle Probleme von Leistungen und Strukturen im Fachgebiet Gynäkologie und Geburtshilfe im Jahr 2011 – allgemeine Aspekte und geburtshilfliche Versorgung. Geburtsh Frauenheilk. 2011.

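### Replacing every missing or doubtful primary VAS value with the study maximum can bias the primary comparison in either direction; small harm if missingness is negligible, but easily avoided

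*Combined protocol and SAP*

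**What the plan says.** The primary endpoint is the severity of intraoperative pain. Methods gives the timing: "Directly after child delivery patients will be first asked about the pain sensation during the delivery according to a VAS scale". Evaluation /Biometrics sets an intention-to-treat analysis in which "all patients who were randomized will be included in the evaluation", and expects that, because recording is so prompt, "only a negligible number of missing values can be assumed". No rate is given.

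For values that are nevertheless absent, the rule is: "In case of doubt or missing values, it will be replaced by the maximum observed VAS values in the study". It does not distinguish arms or reasons. The stated rationale is simplicity; the plan does not claim that the rule is conservative. The next sentence adds: "As sensitivity analyses other imputation methods will be performed". The methods are not named there. Power calculations refers to an attached biometric document that is not among the documents reviewed.

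Two other places bear on the point. Data privacy says that a dropout's data are deleted and left out of the analysis. The description of the course of the study says that surgeons learn the allocation directly before surgery.

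**The concern.** Replacement by the worst observed value looks cautious, but it is cautious about a treatment effect only if it works against the treatment being tested. Here it is applied to both arms, so the arm with more replaced values is usually penalised. An excess of missing scores in control makes pushing look better; an excess in pushing makes it look worse. This happens even when the reason for missingness has nothing to do with pain.

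The trigger is also wider than missingness. Doubt is not defined. It may mean only illegible entries, but as written it lets a recorded score be overwritten with the maximum, and no decision blind to arm is described. The study has one primary endpoint and about 80% power with no allowance for loss, so the primary estimate and p-value would rest directly on this rule.

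**Working it through.** **Inputs from the plan (Power calculations).** Two-sided t-test at 0.05, difference 0.8, SD 2, 100 per arm, 80% power; "we expect higher mean VAS scores between 6-7", taken here as the control mean because the arm is not stated.

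**Assumptions.** A 0-10 scale, so the observed maximum M is 10 (the documents give no range). Missing counts, because the plan gives none. Values missing completely at random, except in step 5.

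**1. The plan's own figure.** Normal approximation: n = 2 × (1.960 + 0.842)² × (2/0.8)² = 98.1, so 99 per arm. The t-based solution is 99.08, so 100 per arm, with 80.4% power. The sample size reproduces.

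**2. Shift per replaced value.** With fractions pC and pP replaced, the difference (control minus pushing) moves by pC(M − μC) − pP(M − μP). At μC = 6.5 and μP = 5.7:

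- each missing control value: (10 − 6.5)/100 = 0.035 in favour of pushing;
- each missing pushing value: (10 − 5.7)/100 = 0.043 against pushing.

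If M were 9, these would be 0.025 and 0.033.

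**3. Simulation with fixed counts.** Normal scores with SD 2, rounded and clipped to 0-10; control mean 6.5; pooled t-test; at least 20,000 trials per row. Rounding and clipping turn the planned 0.80 into 0.78, which is the reference.

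| Missing, control/pushing | Shift by formula | Simulated estimate | Power |
|---|---|---|---|
| 0/0 | 0 | 0.78 | 79% |
| 1/1 | −0.008 | 0.77 | 78% |
| 0/1 | −0.043 | 0.74 | 74% |
| 1/0 | +0.035 | 0.81 | 82.5% |
| 0/2 | −0.086 | 0.69 | 68% |
| 5/5 | −0.040 | 0.74 | 71% |
| 2/6 | −0.188 | 0.59 | 51-52% |
| 5/0 | +0.175 | 0.95 | 92% |

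Analysing observed values instead gives 0.78 with 77% power at 5/5, and 0.78 with 78% power at 2/6. The 74% at 0/1 is the power of a complete trial with 88 per arm.

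With no true effect, type I error under the maximum rule is about 3.5% at 5/5, close to 5% at 0/1 and 0/2, and 8-9% at 5/0 or 0/5. Almost all of those rejections favour the arm with fewer missing values. Mann-Whitney, which the plan also allows, behaves similarly: 73% power at 0/1, 53% at 2/6, and about 8% type I error at a five-value imbalance.

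**4. The plan's own expectation.** Reading negligible as 1% or 2% per arm, with counts varying by chance, power is 77.8% and 75.0% against 78.8% with none missing in the same run. The loss is 1.0 and 3.8 points. Type I error stays at about 5%.

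**5. Missingness driven by pain.** Suppose only scores of 9 or more can be lost. With 30% of those lost in each arm and a true difference of 0.78, the maximum rule gives 0.79 (79% power) and observed values give 0.72 (75%). With no true effect and such losses only in control (about five values), type I error is about 5% under the maximum rule and 8-9% under observed values. The ranking reverses.

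**The case against.** The strongest reply is that pain is asked about immediately after delivery, so few values will be missing, and that maximum replacement guards against the case that matters most: women who gave no score because the pain was severe. Both parts stand. Step 4 shows a small expected cost at 1-2% missing, and step 5 shows that observed values can be the worse choice. The documents do not support the larger imbalances in the table; they show sensitivity and are not forecasts.

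A reader might infer more than the documents support:

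- *That the estimate shifts whenever counts differ.* It need not. At control mean 6.0, six missing in control and five in pushing give 0.06 × 4.0 − 0.05 × 4.8 = 0. Conversely, equal counts do shift the estimate when there is a true effect.
- *That one or two missing values will cost 5 to 11 points of power.* That holds only if the excess falls in pushing. One missing only in control raises power to 82.5%.
- *That the rule generally inflates type I error.* It does so materially only at imbalances of about five values; equal fixed counts lower it.
- *That the plan wrongly calls the rule conservative, or has no sensitivity analysis.* It makes no such claim, and it does promise other imputation methods. They are unnamed in the text supplied; the attached biometric document may say more.

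The promised sensitivity analyses are only a partial answer, because the primary p-value would still come from the maximum rule.

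**Conclusion.** The concern holds in a limited form. As primary handling, study-maximum replacement in both arms makes the estimate depend on the balance of missing counts and can favour either arm when missingness is unrelated to pain. Per replaced value the shift is about 0.035-0.043 points against a planned difference of 0.8. If missingness is as low as the plan expects, the harm is about 1-4 points of power and no type I inflation. With five values missing in one arm only, it becomes material: 0.95 in place of 0.78 if they are in control, and 8-9% type I error whichever arm they are in. The undefined doubt clause is a separate weakness, because it could raise the number of replaced values and touch scores that were recorded.

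These sizes rest on a 0-10 scale, the planning means and SD, and assumed missing counts. Neither the maximum rule nor observed values is safe alone; which performs better depends on why scores are missing. Severity is minor to should-fix. Confidence is high for the mechanism and moderate for the practical impact.

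**What to change.** 1. Remove the doubt clause. State instead: *Recorded VAS values are analysed as recorded; only absent or unreadable values count as missing, and this is decided blind to arm.*
2. Make one prespecified missing-at-random method primary. Observed values are the simplest choice and work with either the t-test or Mann-Whitney.
3. Name the sensitivity analyses:
   - multiple imputation by arm, on the t-test scale, from the later pain scores (a survey at 4-6 hours, and "At day 1 and day 2 postoperatively, patients will fill out the following surveys");
   - maximum VAS in both arms (the current rule);
   - maximum VAS in pushing only;
   - maximum VAS in control only.
4. Report missing counts and reasons by arm, and reconcile the deletion of dropouts under Data privacy with the statement that all randomized patients are analysed. Until that is settled, it is unclear which women the rule covers.

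**Cost.** A few sentences of analysis text and little programming; no new data or patients. The downside is that the primary result then rests on missing at random, which the maximum-VAS analyses probe. Multiple imputation should not be expected to add power over observed values: in a check with one later score (assumed correlation 0.3-0.7) and 2/6 missing, both gave 77-79%, against 51-52% for the maximum rule. Some women may also lack the later scores.

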Study protocol

„Effect of The mother's active pushing
at cesarean delivery “

The target and the reasons for the study

Caesarean section (C-section) is one of the most commonly performed operations for women all over the world. Currently around every 3rd baby (31.3% on average) born in German hospitals is delivered by C-section⁽¹⁾⁽²⁾. Women who deliver by C-section have been reported to express less satisfaction with their birth experience than women delivering vaginally ⁽³⁾. Some women also express strong feelings of loss, failure, and anger during C-section⁽⁴⁾. These feelings are likely related to stress, pain, and fatigue associated with major surgery and the psychological status of the patient and a stressor or trigger in the development of postnatal depression ⁽⁴⁾. Also, some studies suggested that the mother-infant bonding is affected by the mode of the delivery being worse with C-section.

In this study, we will evaluate how the participation of patients in the delivery process during the C-section by pushing will affect the patients' experience. This is done in anticipation that this participation will alleviate the severity of the intraoperative discomfort, the postoperative pain, and improve the breastfeeding and patient's satisfaction by granting the patient a higher feeling of control.

There are different techniques for performing C-Section of which some Techniques are performed with the participation of the mother and others without. Currently, there is no consensus on a standardised technique with convincing evidence of its superiority. The first approach of this modification of the C-section was described in 2008 by Smith et al. and was termed the "natural caesarean" ⁽⁵⁾.

In 2016, a prospective randomised controlled trial was conducted at the Charity Berlin Hospital, aiming to evaluate the safety of patient's delivery experience of the modified C-section (participation of the mother during C-section) and early skin-to-skin contact(STS). Parameters of perinatal outcome for both mother and infant were assessed using modified Likert-Scales and a standardized questionnaire. Primary outcome measures were birth experience and satisfaction for both parents. Parameters of breastfeeding, consecutive problems, APGAR Scores, blood loss and perioperative complications were secondary outcome measures. The trial concluded that birth experiences and

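### The planned ANCOVA on postoperative pain medication groups women by a need-driven, post-randomisation WHO step, so it cannot show what medication does and may distort the arm comparison

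*Combined protocol and SAP*

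**What the plan says.** The last paragraph of Evaluation /Biometrics adds one covariate analysis to the t-test, Mann-Whitney and chi-square comparisons: "We will conduct ANCOVA analyses to see how postoperative pain medication influences the study outcome". The next sentence reads "The WHO pain medication scale will be used to group the patients". The section does not name the outcome, say whether arm is a model term, list other terms, or say how the estimates will be read.

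Three other places bear on it:

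- Methods, on why medication is recorded: "Recording postpartum pain medications is essential as we cannot predict who will require which level of pain relievers". The levels listed are non-opioid, weak opioid and strong opioid.
- Methods, on the primary endpoint: "Directly after child delivery patients will be first asked about the pain sensation during the delivery according to a VAS scale".
- The target and the reasons for the study, on what pushing is expected to do: "this participation will alleviate the severity of the intraoperative discomfort, the postoperative pain". Postoperative pain is also a listed secondary endpoint.

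Surgeons learn the allocation directly before the operation (A detailed description of the course of study), so any postoperative analgesic comes after randomisation.

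**The concern.** ANCOVA is safe in a randomised trial when the covariate is fixed before treatment. WHO step is not. It is a response to pain, and pain is what the trial measures. Three problems follow, depending on what the unnamed outcome and model turn out to be.

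1. If the outcome is the primary VAS, it is asked directly after delivery. Medication given afterwards cannot influence it, and any association runs the other way.
2. If the outcome is related to postoperative pain, women in more pain reach higher steps. The step coefficient is confounded by indication even if pushing does nothing.
3. If arm is in the model and pushing changes postoperative pain or medication need, conditioning on step removes or distorts part of the arm difference. The protocol itself expects an effect on postoperative pain.

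At stake is a secondary report in which analgesia looks weak or harmful, or an adjusted arm difference that is taken for the effect of pushing.

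**Working it through.** **The plan's own figure.** For a difference of 0.8, SD 2, two-sided 0.05 and 80% power: n = 2 × (1.960 + 0.842)² × (2/0.8)² = 98.1, so 99 per arm by the normal approximation. The exact t solution is 99.08, so 100 per arm, with power 80.4%. The stated 100 reproduces, and nothing below touches it. The plan gives no figure for the ANCOVA.

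**Inputs from the documents.** SD 2. The reference trial's 6-hour pain: "the mean VAS scores at 6 hours ranged between 3.4 and 3.9 with a standard deviation of 1.7-2.0". Expected effect 15-20%. Applying that effect to the 6-hour means gives a postoperative benefit of 0.15 × 3.4 = 0.51 to 0.20 × 3.9 = 0.78 points.

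**Assumed, because the documents are silent.** Correlation between intraoperative and postoperative pain 0.3, 0.5 or 0.7; step shares 50/35/15%; step set by cutting (postoperative pain before relief + noise of SD 1, 2 or 4); relief of 1 or 2 points per step. The model is least squares of pain on arm plus two step indicators, with 4,000,000 simulated women per scenario.

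**Step coefficient, postoperative pain, top versus bottom step (benefit 0.51).** The fitted value is the confounding part minus the true relief (2 or 4 points over two steps):

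| Noise SD | Confounding part | 1 point per step (truth -2) | 2 points per step (truth -4) |
|---|---|---|---|
| 1 | +4.22 | +2.22 | +0.22 |
| 2 | +3.34 | +1.34 | -0.66 |
| 4 | +2.11 | +0.11 | -1.89 |
| 2, half the steps routine | about +1.7 | -0.29 to -0.35 | -2.29 to -2.35 |

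The last row spans three step splits and benefits of 0.51 and 0.8. The bias is always towards more medication, more pain. The sign reverses in four of the six fully need-driven cells and in neither half-routine cell.

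**Arm difference on the primary VAS, if arm is in the model.** In least squares, unadjusted difference = adjusted difference + Σ (step coefficient × arm difference in that step's share). Take benefit 0.51, correlation 0.5, noise 2. The middle-step share is 0.365 in controls and 0.335 with pushing; the top-step share is 0.171 and 0.129. The step coefficients are 0.90 and 1.66. The sum is 0.90 × (-0.030) + 1.66 × (-0.042) = -0.097, so the adjusted difference is -0.80 + 0.097 = -0.70. The full set, for a true difference of -0.80:

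| Benefit | Noise SD | Correlation 0.3 | 0.5 | 0.7 |
|---|---|---|---|---|
| 0.51 | 1 | -0.709 | -0.647 | -0.585 |
| 0.51 | 2 | -0.744 | -0.705 | -0.667 |
| 0.51 | 4 | -0.779 | -0.764 | -0.749 |
| 0.78 | 1 | -0.660 | -0.565 | -0.471 |
| 0.78 | 2 | -0.713 | -0.654 | -0.595 |
| 0.78 | 4 | -0.767 | -0.744 | -0.721 |

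For a true difference of zero, add 0.80 to each cell: +0.02 to +0.33 against pushing. With half the steps routine (correlation 0.5, noise 2, benefit 0.51 or 0.8) this falls to +0.01 to +0.04. With no postoperative effect of pushing, the arm bias is zero within simulation error.

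**Arm difference on postoperative pain (benefit 0.51, noise 2).** Unadjusted it is -0.40 at 1 point relief per step and -0.28 at 2 points; step-adjusted it is -0.32 in both cases. At 2 points the adjusted figure is nearer the underlying -0.51.

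**The case against.** The best case for leaving the text alone is that this is two sentences on a supplementary question, and that the plan never promises a medication-adjusted effect of pushing. Arm may not be in the model, and the outcome may be postoperative pain rather than the primary VAS. On that view the documented fault is only under-specification. That argument makes problems 1 and 3 conditional, and they are stated so. It leaves problem 2, which follows from the stated purpose and the stated grouping alone.

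The magnitudes are also assumed. The 15-20% was expected for intraoperative pain, and the 6-hour means come from women already receiving analgesia, so the 0.51-0.78 range is an extrapolation. This stands: the sizes are illustrative.

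Part of the step may be routine, since the protocol says of the reference trial: "This study reflects the routine pain medication used in our clinics and was therefore selected". With half the steps routine (noise 2, benefit 0.51), the adjusted postoperative arm difference is -0.46, against -0.45 and -0.39 unadjusted at 1 and 2 points relief. With 80% routine it is -0.50, against -0.49 and -0.46. Adjustment is then slightly nearer the underlying effect. This also stands, and it means adjustment is not always the worse choice. It still estimates a different quantity from the randomised effect. Routine use shrinks the confounding of the step coefficient without changing its direction, and the protocol expects levels to vary between women.

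**Conclusion.** The concern holds. Followed as written, the ANCOVA cannot answer its own question, because the step coefficient carries the reason for escalation as well as the drug effect. In the scenarios run, that moves the top-versus-bottom contrast by about 2.1 to 4.2 points when steps are fully need-driven, and by about 1.7 points when half are routine. A reversed sign is possible but not certain. Distortion of the arm difference requires arm in the model and an effect of pushing on postoperative pain or need; without both there is none. All sizes rest on assumed correlation, step distribution, need-driven share and relief; the direction of the step bias requires only that women in more pain tend to reach higher steps. The planned unadjusted primary comparison is sound. This is an inexpensive improvement to a secondary analysis that should be made before the data are seen.

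**What to change.** Replace the two ANCOVA sentences with three statements.

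1. The primary endpoint is not adjusted for postoperative medication.
2. The highest WHO step reached within a stated recording window is compared between randomised arms with an ordinal method (proportional-odds model or Mann-Whitney test) and read alongside the unadjusted postoperative pain comparison. Methods gives no window for medication; days 0-2 would match the pain assessments under Measurements, findings and observations.
3. Any retained medication-adjusted analysis of postoperative pain has its outcome and model terms fixed in advance, is labelled exploratory, and is presented neither as a treatment effect nor as a medication effect.

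Items 1 and 3 are the minimum and cost only wording. Item 2 is the randomised comparison of analgesic use and adds one secondary outcome from data already to be recorded. Its power at 100 per arm is low: about 10-28% at a postoperative benefit of 0.51 and 19-59% at 0.8, over noise SD 4 to 1. A non-significant result would therefore not show equal use.

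The unadjusted postoperative difference has its own limit. If relief is 1-2 points per step, differential analgesic use dilutes 0.51 to 0.22-0.44 and 0.78 to 0.34-0.67. Reading it as the effect of pushing regardless of analgesic use is a defensible choice, not the only one, and the plan should say which it makes.
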